Methods and Analysis: This will be a single center prospective before-and-after proof-of-concept study. Adults (18 years and older) undergoing elective surgery and recovering in two selected PACU bays will be enrolled. During the initial 3-month observation phase, clinicians in the telemedicine center will not communicate with clinicians in the PACU, unless there is a specific patient safety concern. During the subsequent 3-month interaction phase, clinicians in the telemedicine center will provide structured decision support to PACU clinicians. The primary outcome will be time to PACU discharge readiness determination in the two study phases. The attitudes of key stakeholders towards the telemedicine center will be assessed. Other outcomes will include detection of physiological derangements, complications, adverse symptoms requiring treatments, and emergencies requiring medical intervention.

Registration Information: This trial is registered on clinicaltrials.gov, NCT04020887

Keywords:

Telemedicine, Post-Anesthesia Care Unit, Protocol, Proof-of-Concept, Observational Study

Introduction

After invasive procedures in the operating room (OR) or other procedure rooms, patients are usually transferred to a post-anesthesia care unit (PACU) for high acuity monitoring. The PACU period is important for patients, especially since they often are still in a vulnerable state.^{1,2} Patients are prone to peri-procedural and post-anesthetic complications including dehydration, anemia, coagulopathy, bleeding, hypothermia, delirium, respiratory depression, airway obstruction, bronchospasm, hypotension, kidney injury, arrhythmias, metabolic acidosis, hypoxemia, glucose and electrolyte abnormalities, atelectasis, and pulmonary edema.^{3,4} These complications must be recognized and appropriately managed by PACU clinicians. Furthermore, PACU clinicians need to identify and manage patients' adverse symptoms including pain, nausea, urine retention, weakness, and itching, which are common after invasive procedures, whether with or without general anesthesia.

The ideal PACU environment provides close monitoring and prompt rescue for peri-procedural complications, while also efficiently transferring patients to their next phase of care. For example, when patients deteriorate in the PACU, it is important to recognize this early, intervene appropriately, and arrange transfer to a higher acuity area, such as an intensive care unit, when warranted.

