This proof-of-concept study has been reviewed and granted a waiver of informed consent for all subjects enrolled by the Human Research Protection Office at Washington University in St. Louis (HRPO#201901180) and is registered at clinicaltrials.gov (NCT04020887). It is infeasible to conduct this proof-of-concept study without a waiver of consent. Additionally, this study has been determined to involve no more than minimal risk to participants, as study participation would not deviate from or delay current standards of peri-anesthesia care. Both the “Good ReseArch for Comparative Effectiveness” (GRACE) checklist⁷ and PICOTS framework⁸ (Table 1) were used in designing this study.

The conduct and reporting of this observational study will follow the “Reporting of studies Conducted using Observational Routinely-collected health Data” (RECORD)⁹ statement and the “Strengthening the Reporting of Observational Studies in Epidemiology” (STROBE)¹⁰ statement guidelines for reporting observational studies.

[figure not shown]
Table 1. PICOTS Framework

PICOTS typology for a comparative effectiveness research protocol	
Population	Adult (18 years and older) patients undergoing elective surgery
Intervention	Telemedicine center for PACU
Comparator	Current post-anesthesia care unit practice
Outcomes	(i) potential utility, and (ii) acceptability of integrating telemedicine in the post-anesthesia care unit environment
Timing	6-month study duration

Setting	Hospital environment – Barnes-Jewish Hospital, St. Louis, Missouri
---------	--

Primary Intervention: Telemedicine Center for PACU

Two bays in Barnes Jewish Hospital (BJH) in St. Louis, Missouri, will be equipped for telemedicine interaction (Figure 1). Video cameras and monitors have been installed in each of these bays to allow for remote monitoring, as well as two-way video communication during the interaction phase. The telemedicine center is staffed by attending anesthesiologists along with certified registered nurse anesthetists (CRNAs), anesthesiology residents, and student registered nurse anesthetists (SRNAs), and is currently providing evidence-based support to clinicians in the operating rooms.^{11–14}

Two PACU bays located across from nurse's station

High-resolution camera for patient monitoring and communication

Ultra-sharp monitor on telescoping arm for two-way patient communication

High-definition microphone for patient monitoring and communication

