In the first three months (the Observation phase) of this proof-of-concept study, a telemedicine center for the PACU will monitor patients assigned to two PACU bays. Both the telemedicine center and nurses caring for patients in the PACU bays will separately document physiological derangements (Table 2), treatable symptoms (Table 3), or a situation requiring urgent medical intervention (telemedicine center only; Table 4) during the PACU stay. Clinicians in the telemedicine center will assess when the patient meets discharge criteria, based on the modified Aldrete scale¹⁵ and their clinical judgment. They will document the time that discharge criteria are met, the modified Aldrete scale score at this time, and any additional relevant information. If clinicians in the telemedicine center judge that they are unable to determine a patient's readiness for discharge, they will document their reasons (Table 5). Clinical judgment will be used in determining appropriate discharge parameters for patients with pre-existing conditions. The telemedicine center clinicians will document each patient's information outlined in Tables 2-5 directly into REDCapTM (a secure web application for managing online surveys and databases) and AlertWatch. After a patient has been discharged from the PACU, the PACU nurse will fill out a form providing information outlined in Tables 2-5. This includes

information on physiological derangements, treatable symptoms, and discharge information. This form will be collected by the research team, and the information in the form will be documented in REDCap. During this phase of the study, clinicians in the telemedicine center will not communicate with clinicians in the PACU (nurses or physicians), unless there is a patient safety event.

Table 2. Physiological derangements and complications

Did the patient have any of the following physiological derangements:	Definition: (for study purposes)
Persistent confusion / delirium	
Tachycardia	HR >120/min
Bradycardia	HR <45/min
New onset atrial fibrillation	
Respiratory depression	<8 respirations per minute
Hypoxemia	<90% O ₂ Saturation
Hypotension	MAP <55
Weakness	<5/5 power in limbs
Emesis / vomiting	
Hyperglycemia	Glucose >200mg/dL
Hypothermia	Temperature < 35.5 C
Low urine output (for PACU stay >4h)	<0.5 ml/kg per hour

Table 3. Symptoms requiring treatment

Did the patient complain of the following symptoms:	
Dizziness or lightheadedness	Difficulty breathing
Nausea	Shivering

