Severe pain (Numerical Rating Scale >7/10)	Itching
Chest pain unrelated to surgery	

Table 4. Emergency medical interventions

Did the telemedicine center contact PACU clinicians for any of the following interventions:	
Intubation	Unplanned transfusion
Assisted ventilation	Naloxone administration
Cardiopulmonary resuscitation	Return to OR
Cardioversion	Other (free text box)
If Yes, please check all that apply:	
 PACU nurse already aware of the situation	
 PACU nurse unaware of the situation	
 PACU nurse disagreed with the assessment	
 PACU nurse had already spoken to the supervising physician regarding the situation	

Other (please describe):

*Only the telemedicine center will document the detection of urgent situations.

Table 5. Patient discharge readiness

At what time did the patient sufficiently recover to be discharged (case attending anesthesiologist contacted for discharge)?	
PACU Nurses	Telemedicine Center for PACU
Time anesthesiologist is contacted for discharge evaluation	Time ready for discharge
Aldrete Score at discharge	Aldrete Score at discharge
	Unable to determine patient's readiness for discharge
Modified Aldrete Scale Component and Scoring Parameters	If Unable to fully assess, select reason(s) why (Checkbox)
Respiration	 More patient information needed  Equipment issues  Patient cooperation  Other (free text box)
2 – Able to take deep breath and cough	
1 – Dyspnea / Shallow Breathing	
0 – Apnea	
O₂ Saturation	
2 – Maintains > 92% on room air	
1 – Needs O ₂ inhalation to maintain O ₂ saturation > 90%	
0 – Saturation <90% even with supplemental O ₂	
Consciousness	
2 – Fully awake	
1 – Arousable on calling	
0 – Not responding	
Circulation	
2 – BP ± 20mmHg pre-op	
1 – BP ± 20-50mmHg pre-op	
0 – BP ± greater than 50mmHg pre-op	
Motor Activity	
2 – Able to move 4 extremities voluntarily or on command	
1 – Able to move 2 extremities voluntarily or on command	
0 – Able to move 0 extremities voluntarily or on command	

Interaction Phase (3 months)

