This is a proof-of-concept study and will only address surrogate outcomes. The primary outcome (time to PACU discharge readiness) will use two comparison groups. First, historical controls will be drawn from the observation phase. A propensity score for inclusion into the study will be generated as a function of (minimally) surgery performed, day of week, time of day, age, and sex. 3:1 matched control patients will be included. The outcome will be analyzed with interrupted time series methods with flexible functions of calendar time used to adjust for secular trends; the study hypothesis is a non-zero discontinuity at telemedicine implementation.

That is, if Y_i is the outcome for the i th patient at time t_i with covariate vector X_i , while the implementation time is t_0 , and $I()$ is the indicator function,

$$Y_i = f_1(t_i)I(t_i < t_0) + f_2(t_i)I(t_i \geq t_0) + X_i\beta + \epsilon H_0: f_1(t_0) = f_2(t_0)$$

where f_1 and f_2 are smooth functions. Other patient factors known to strongly influence PACU length of stay (age, ASA physical status, number of co-morbidities, morbid obesity, obstructive sleep apnea, surgical specialty, primary anesthesia type, history of postoperative nausea and vomiting, preoperative pain, and scheduled case duration) will be included as covariates. The minimization criteria will be least squares or trimmed least squares or other robust criteria if there are substantial outliers. Outcomes will be examined for residual auto-correlation, and if non-negligible, auto-correlation robust standard errors (such as Newey-West errors) and an ARIMA model will be reported. Confidence intervals will be generated by non-parametric bootstrap sampling where possible. No adjustment will be made for matching, but bootstrap methods will respect the matched “units.” P-values will be generated both by likelihood ratio tests and by using non-deployment times as a null distribution; that is, we will run the same analysis looking for discontinuity at times remote from the true implementation time. We will conduct sensitivity analyses with transformations of the outcome variable. We will use an excluded run-in period of 1 month as a sensitivity analysis. Because hospital length of stay is unlikely to be meaningfully affected by a telemedicine center for the PACU, but does track overall acuity and surgical severity, we will use hospital length of stay as a control time series.

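### Table 2 counts any limb power below 5/5 as weakness, so the agreement result for that item may mix expected or old weakness with new, unexpected weakness

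*Combined protocol and SAP*

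**What the plan says.** Table 2 (Physiological derangements and complications) asks "Did the patient have any of the following physiological derangements" and defines weakness only as "<5/5 power in limbs". Nothing there or elsewhere in the protocol limits this to new or unexplained weakness. Two comparable items are limited: "New onset atrial fibrillation" in Table 2 and "Chest pain unrelated to surgery" in Table 3.

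The one allowance for prior illness, under Observation Phase, reads "Clinical judgment will be used in determining appropriate discharge parameters for patients with pre-existing conditions". It concerns discharge, not the Table 2 items.

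Table 1 gives the population as "Adult (18 years and older) patients undergoing elective surgery", with no exclusion by anesthetic or neurological baseline. The Introduction speaks of symptoms after procedures "whether with or without general anesthesia". The covariates for the primary outcome include "surgical specialty, primary anesthesia type, history of postoperative nausea and vomiting", so the plan expects anesthesia type to vary.

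Aim 1a is judged in the observation phase by comparing the nurse's and the telemedicine center's forms for each patient. Under Statistical Methods, Secondary Outcomes, each item is reduced to present or absent, cross-tabulated, and summarized by a Jaccard index. No split by anesthetic or baseline deficit is planned.

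**The concern.** Aim 1a asks whether remote clinicians can identify derangements while they are occurring. A limb still weak from a block, or weak since before surgery, meets the weakness rule as written, yet it is not the event of interest. The remote team works from the electronic record, waveforms and video, and two-way video is described for the interaction phase only. It is a reasonable inference that in the observation phase some such patients could be marked from the chart.

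Applying the same rule to both recorders does not cancel the problem. The Jaccard index ignores patients whom neither recorder marks, so shared expected positives enter the numerator directly. If instead one recorder counts expected weakness and the other does not, the rule creates disagreement unrelated to detection. The displayed counts do not separate the two kinds of weakness, so a reader could not tell which had happened.

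**Working it through.** **The plan's own figure.** The only power statement concerns the primary outcome: a 20 min difference, SD 65 min, 250 patients per phase. The standard error is 65 × √(2/250) = 5.81 min, and 20/5.81 = 3.44. Two-sided power is Φ(3.44 − 1.96) = 93.1% at alpha 0.05 and Φ(3.44 − 2.81) = 73.7% at alpha 0.005. Both stated bounds (>90% and >70%) reproduce. The weakness item does not enter this calculation. No figure is stated for Aim 1a.

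**Direction of the effect.** Jaccard = (marked by both) / (marked by either). For two groups of patients pooled, J = (both₁ + both₂) / (either₁ + either₂), an average of the two groups' indices weighted by the number marked by either. Adding expected weakness therefore pulls the index toward the agreement on expected weakness. It rises if that agreement is the higher of the two and falls if it is the lower.

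**Illustration with counts.** All counts are assumed, because the documents give none. Five of the 250 patients in the phase have unexpected weakness marked by at least one recorder; 10, 25 or 50 further patients have expected weakness and are marked by at least one.

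| Unexpected weakness alone | Expected weakness marked by | +10 | +25 | +50 |
|---|---|---|---|---|
| 1/5 = 0.20 | both, always | 11/15 = 0.73 | 26/30 = 0.87 | 51/55 = 0.93 |
| 1/5 = 0.20 | both in half, one in half | 6/15 = 0.40 | 13.5/30 = 0.45 | 26/55 = 0.47 |
| 4/5 = 0.80 | both in half, one in half | 9/15 = 0.60 | 16.5/30 = 0.55 | 29/55 = 0.53 |

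Half-counts are expected values. The first two rows rise because they start from 0.20; the third falls because it starts from 0.80.

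**Illustration with rates.** Let w and b be the prevalences of unexpected and expected weakness, with recorders marking independently. The nurse detects 80% and telemedicine 40% of unexpected weakness. Expected weakness is marked with probabilities qₙ (nurse) and qₜ (telemedicine). Then

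J = [w(0.8 × 0.4) + b·qₙqₜ] / [w(0.8 + 0.4 − 0.32) + b(qₙ + qₜ − qₙqₜ)].

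With b = 0, J = 0.32/0.88 = 0.36. For w = 2% and b = 10%:

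- Both mark from the record (0.95 each): (0.0064 + 0.09025) / (0.0176 + 0.09975) = 0.82.
- Nurse marks, telemedicine does not (0.9 and 0.1): (0.0064 + 0.009) / (0.0176 + 0.091) = 0.14.
- Both mostly treat it as expected (0.1 each): (0.0064 + 0.001) / (0.0176 + 0.019) = 0.20.

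Over w from 1% to 5% and b from 5% to 30%, the three cases span 0.65-0.89, 0.11-0.23 and 0.09-0.31, against 0.36 with expected weakness excluded.

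**The case against.** The documents never mention a regional, neuraxial or nerve block and give no rate of blocks or prior deficits. Varying anesthesia type could mean general anesthesia versus sedation. This stands, and the point is conditional for that reason. A reader might infer that the weakness result does in fact measure knowledge of the anesthetic; the documents show only that it could.

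A reader might also infer that every patient with a block or an old deficit meets the definition. That is too strong: power must actually be below 5/5 in the PACU. Nor is inflated agreement a safe inference, since the index falls in several of the cases above.

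Cause-neutral cut-offs are common in Table 2. A known diabetic with glucose above 200 mg/dL also counts, and the record is a designated source of information for the telemedicine center. This weakens any claim that the weakness item is uniquely defective. It does not explain why atrial fibrillation and chest pain were qualified and weakness was not.

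Finally, the plan admits that the accuracy of these assessments is hard to analyze, tests no agreement or superiority hypothesis, shows the full counts, and sets no numerical threshold for success. All of that limits the consequence. The plan's caveats concern the bedside standard, false positives and timing, not expected weakness. The forms themselves are to be supplied as supplementary files, so any instruction on this item that they contain could not be checked.

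**Conclusion.** The point holds as a minor and conditional one. As written, the definition does not separate expected or long-standing weakness from new, unexpected weakness, and the planned tabulation does not separate them afterwards. If patients with such weakness are treated in the two bays, the index for this item depends partly on how many there are and how each recorder reads the rule. If they are few, the effect is small. The size and direction are unknown, and every Jaccard value above rests on assumed inputs. It is a matter of interpreting one secondary item: no decision rule depends on it, and the primary analysis and sample size stand.

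**What to change.** Keep the item and the forms as they are. In the Secondary Outcomes tabulation, add one line: the weakness confusion matrix and Jaccard index will be reported for all patients, and again without patients who had a regional or neuraxial technique or a documented preoperative deficit. Interpret Aim 1a for weakness from both tables.

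Identify these patients from the perianesthesia information and clinical history that the Data Collection section says are captured from Epic. Primary anesthesia type alone may miss a block added to a general anesthetic. The documents do not list the perianesthesia fields, so confirm that block use is among them.

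Two other remedies are less good. Using only the restricted table would discard new weakness arising in patients who had a block or a prior deficit. Rewording the item to new, unexplained weakness would ask each recorder to judge cause, which could itself add disagreement between recorders.

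The cost is one sentence in the plan and one extra table, with few events in the restricted version.

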In the three months following the observation phase, clinicians in the telemedicine center will interact with patients and clinicians associated with the designated PACU bays using audio-visual technology. PACU clinicians and clinicians in the telemedicine center will become a “fused” team, and the telemedicine center will continue to document information on physiological derangements (Table 2), treatable symptoms (Table 3), situations requiring urgent medical intervention (Table 4), and discharge readiness (Table 5).

The telemedicine center clinicians will assess patients’ discharge readiness throughout their PACU stay. A modified Aldrete scale along with clinical judgment will guide the telemedicine center clinicians in determining readiness for discharge (Table 5). After discharge readiness has been determined by the telemedicine center, the attending anesthesiologist in the telemedicine center will document discharge readiness in AlertWatch and REDCap, and contact the relevant anesthesiologist. The telemedicine center for PACU will document when this information was communicated. At any point clinicians in the telemedicine center might decide to contact PACU clinicians (nurse or physician) if they have specific concerns regarding patients. If the telemedicine center clinicians feel that they cannot adequately assess a patient’s clinical status, they will notify the PACU clinicians. This will be documented together with a relevant explanation (Table 5).

Final determination and sign-off regarding discharge suitability will be made by the anesthesiologist in the PACU. With this proof-of-concept research project, there will be no change in relation to which clinicians have responsibility for decision making and clinical care. The telemedicine center clinicians will not write any orders in the medical record, and will provide opinions only to physicians and nurses who are responsible for patient care in the

PACU. The responsibility to call for help when patients are deteriorating will remain with the PACU nurses, as is the current standard in that environment. The notion is that the telemedicine center will not lead to any decrement in the care that PACU patients are currently receiving from nurses and physicians in that environment.

The successful integration of the telemedicine center into each of the core PACU functions will be measured in the following ways:

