The accuracy of physiologic, symptom, and status assessments is less straightforward to analyze. At the heart of the proposal is the belief that telemedicine assistance will detect some abnormalities not caught (or caught later) by the bedside team and detect that the patient has adequate status for PACU discharge before the bedside nurse. Using the bedside assessment as a gold standard is therefore limited. Similarly, although we believe that abnormalities detected by either bedside or telemedicine are unlikely to be false positives, we have no way of assuring that. We also cannot reliably determine the timing of the bedside nurse's detection of an abnormality, as they may document it much later if they believe it does not require an immediate intervention.

Each status assessment event can occur multiple times for each patient; however, we are unlikely to accurately capture the bedside nurse's impression of the number of times an event occurred. We will therefore binarize the presence of each assessment type and display confusion matrices (count tabulations) for each assessment type, which we will summarize with Jaccard indices. The "null hypothesis" that these measures do not agree at all is not meaningful or the subject of this study. As described above, neither is a directional superiority hypothesis possible to evaluate. Final Aldrete scores will be assessed with pearson correlation, and a t-test of the difference in scores presented. Differences in ready-for-discharge times will be summarized as mean and standard deviation, with the null hypothesis of zero mean tested by t-test with a robust standard error.

Agreement of emergency medical status is unlikely to have enough events to be statistically compared. We will present cross-tabulations of (emergency detected by telemedicine center:

yes/no) and (PACU nurse: disagree, investigate and agree, already aware, physician contacted). The absolute rate of telemedicine center false positives (team disagrees), true positives (team unaware), true positives (team aware), and false negatives (team aware > 15 minutes prior or t never detects) will be presented with 95% confidence intervals.

Data Collection

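### Table 5 has no entry for a patient telemedicine still judged not ready at departure, so the paired readiness-time test leans toward telemedicine being earlier

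*Combined protocol and SAP*

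**What the plan says.** Table 5 gives each side its own column. The nurse records "Time anesthesiologist is contacted for discharge evaluation". Telemedicine records "Time ready for discharge" and an Aldrete score, or else "Unable to determine patient's readiness for discharge". The reasons (more information needed, equipment, cooperation, other) are introduced by "If Unable to fully assess, select reason(s) why (Checkbox", so they apply only when assessment was not possible.

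The Observation Phase section has the same two branches. When criteria are met, "They will document the time that discharge criteria are met, the modified Aldrete scale score at this time, and any additional relevant information". When readiness cannot be determined, the reasons are recorded. In that phase telemedicine does not contact the bedside unless there is a patient safety event. The Interaction Phase section says that "Final determination and sign-off regarding discharge suitability will be made by the anesthesiologist in the PACU", and that the study changes nothing about who is responsible for decisions.

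Under Statistical Methods, Secondary Outcomes: "Differences in ready-for-discharge times will be summarized as mean and standard deviation, with the null hypothesis of zero mean tested by t-test", using a robust standard error. No section says what to do when the telemedicine time is missing or censored by departure.

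**The concern.** A paired difference needs two times. If telemedicine can assess the patient, judges the patient not yet ready, and the patient then leaves, telemedicine never reaches a ready time. Judgments that would have come after departure are therefore cut off, and no matching limit applies to early ones. The loss is one-sided.

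The Secondary Outcomes section says the proposal rests on the belief that telemedicine will recognise readiness before the bedside nurse, and the truncation pushes the estimate the same way. Identifying discharge readiness is also a stated success measure for the observation phase. The patients affected are those who left while telemedicine judged them not ready, which is the disagreement a reader would most want counted. For emergencies the plan reports false positives and false negatives; for discharge readiness it has no counterpart.

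**Working it through.** **The plan's own figure first.** The documents give no power or precision for the paired readiness-time test. The nearest stated figure is the primary power: 250 per phase, 20 min difference, SD 65 min. SE = 65 × √(2/250) = 5.81 min and 20/5.81 = 3.44. Two-sided power is Φ(3.44 − 1.96) = 93.1% at alpha 0.05 and Φ(3.44 − 2.81) = 73.7% at alpha 0.005. Both agree with the stated >90% and >70%. Nothing below changes them.

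**Set-up for the paired test.** Let D be telemedicine ready time minus the nurse's call time, and L the lag from that call to departure.
- From the documents: 250 patients in the phase; the nurse-side time is the call to the anesthesiologist; the telemedicine time exists only if telemedicine judged the patient ready.
- Assumed, because the documents give neither: D is normal with SD s, and L takes a range of values. The true mean of D is set to 0, so the null hypothesis holds.
- Judgments between the call and departure (0 < D ≤ L) are kept. Only D > L is lost.

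For scale, if each side's time had the plan's SD of 65 min, s = 30 would imply a correlation of 1 − 30²/(2 × 65²) = 1 − 900/8450 = 0.89 between them.

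**Fixed lag.** Fraction lost = 1 − Φ(L/s). Bias of the mean = −s × φ(L/s)/Φ(L/s).

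Example, s = 30 and L = 30: lost = 1 − 0.841 = 16%; bias = −30 × 0.242/0.841 = −8.6 min.

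| s (min) | L (min) | Lost | Bias (min) | Test rejects a true null |
|---|---|---|---|---|
| 30 | 15 | 31% | −15.3 | 100% |
| 30 | 30 | 16% | −8.6 | 100% |
| 30 | 45 | 7% | −4.2 | 67% |
| 30 | 60 | 2.3% | −1.7 | 14% |
| 30 | 90 | 0.1% | −0.1 | 5% |
| 15 | 15 | 16% | −4.3 | 100% |
| 15 | 30 | 2.3% | −0.8 | 13% |
| 45 | 30 | 25% | −19.2 | 100% |
| 45 | 60 | 9% | −8.1 | 90% |
| 45 | 90 | 2.3% | −2.5 | 15% |

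Rejection rates come from 3,000 simulated t-tests, except the 45 min row, which uses a normal approximation.

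**Variable lag.** With exponential lags of mean 30 min and L independent of D, s = 15, 30 and 45 give biases of −3.1, −10.3 and −19.7 min, with rejection of 91%, 100% and 100%. With s = 30 and mean lag 60 min, 15% are lost, the bias is −6.2 min and rejection is 91%.

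**If departure time is entered instead of dropping the patient.** With s = 30 and exponential lag of mean 30, the bias is −4.9 min instead of −10.3. It is roughly halved but keeps its direction.

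**If the missing category is recorded.** Departure does not come before the call (L ≥ 0), so a patient judged not ready at departure has D > 0 and the sign of the difference is known. A sign test on all 250 patients, with these counted as telemedicine later, rejects a true null 4.8% of the time.

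**The case against.** The case against has real force on strength and size.

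- **Frequency.** A reader might infer that this outcome is certain to occur. No section gives a frequency, departure needs both a call and a sign-off, and judgments between call and departure survive. What can be said is that it is to be expected: the Introduction itself says throughput pressure sometimes moves patients out before they have recovered sufficiently.
- **Recording.** A reader might infer that the disagreement vanishes. The *Other* free-text box or the provision for additional information could hold a note, a safety event permits contact, and the actual REDCap form is not shown. That stands, but none of these routes yields a time for the t-test.
- **Exclusion is inferred.** The plan does not say that such patients are dropped; it gives no rule. This also stands. Without a time they cannot contribute a difference, and substituting departure time leaves about half the bias in the scenarios run.
- **Early judgments.** It would be too strong to say that every earlier difference is kept. Patients whose readiness truly could not be determined also lose their time, in an unknown direction.
- **Size.** The documents do not support saying that two equally fast raters would always give a significant result. At lags of about 3 SDs or more the bias is near zero. The nurse's call and telemedicine readiness are also different events. If the call trails readiness, less is truncated: with an assumed mean of −20, SD 30 and lag 30, 4.8% are lost and the bias is about −3.1 min.
- **Aldrete scores.** Whether the Aldrete comparison loses the same patients is unclear. The Observation Phase section ties the telemedicine score to the time criteria are met, while Table 5 labels it as at discharge.

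**Conclusion.** The point holds for structure and direction. As written, the form has no entry for *assessed, not ready at departure*, the analysis has no rule for it, and the resulting loss can only favour telemedicine being earlier. Substituting departure time does not cure it.

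The size cannot be derived from the documents. Across the table it runs from −0.1 to −19.2 min, depending on an assumed SD of the paired difference and an assumed lag, with a true difference of 0 and normal differences. At SD 30 min it is about −15, −9 and −2 min at lags of 15, 30 and 60 min.

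This concerns one secondary comparison in a proof-of-concept study. It does not touch the primary power calculation. It is worth fixing before data collection, because a judgment that was not recorded cannot be recovered afterwards.

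**What to change.** 1. In the telemedicine column of Table 5, add the option *not ready when patient left PACU*, with the telemedicine Aldrete score at departure. Take departure time from the EHR.
2. In Secondary Outcomes, for the observation phase, add or substitute a sign test that counts these patients as telemedicine later. As a sensitivity analysis, fit a model for the paired difference that right-censors them at departure; if it is a normal model, state that assumption. The observation phase is the right place, because in the interaction phase the two teams communicate and their times are no longer independent.
3. Report the number and percentage of patients in the new category and, separately, in the existing unable-to-determine category.
4. State at which moment the telemedicine Aldrete score is taken, so that the Observation Phase text and Table 5 agree.

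The cost is one more form field, a little more analysis, and probably a smaller apparent telemedicine lead. Clinical care does not change.
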